9.2.2 Sensitivity Analysis of Primary Efficacy Variables

The primary analysis for point estimate and CI will be repeated using Observed Cases without any imputation as a sensitivity analysis. This will be conducted on the FAS based on randomized treatment groups.

Supportive NRI analysis will also be conducted on the Per Protocol Analysis Set.

9.2.3 Key Secondary Efficacy Analyses

Ranked key secondary endpoints (Upadacitinib versus placebo if not otherwise specified) for US/FDA regulatory purposes are:

1. Change from baseline in DAS28 (CRP) at Week 12;
2. Change from baseline in mTSS at Week 26;
3. Change from baseline in HAQ-DI at Week 12;
4. ACR50 response rate at Week 12 (non-inferiority of Upadacitinib vs ADA);
5. Change from baseline in SF-36 Physical Component Score (PCS) at Week 12;
6. Proportion of subjects achieving LDA based on DAS28 (CRP) ≤ 3.2 at Week 12;
7. Proportion of subjects achieving CR based on DAS28 (CRP) at Week 12;
8. Proportion of subjects achieving LDA based on CDAI ≤ 10 at Week 12;
9. Change from baseline in morning stiffness (duration) at Week 12;
10. Change from baseline in FACIT-F at Week 12;
11. ACR50 response rate at Week 12 (superiority of Upadacitinib vs ADA);
12. Change from baseline in patient's global assessment of pain at Week 12 (superiority of Upadacitinib vs ADA);

13. Change from baseline in HAQ-DI at Week 12 (superiority of Upadacitinib vs ADA).

Other key secondary endpoints (Upadacitinib versus placebo if not otherwise specified) for US/FDA purposes are:

1. ACR50 response rate at Week 12
2. ACR70 response rate at Week 12
3. Proportion of subjects with no radiographic progression (defined as change from baseline mTSS ≤ 0) at Week 26

Ranked key secondary endpoints (Upadacitinib versus placebo if not otherwise specified) for EU/EMA regulatory purposes are:

1. Change from baseline in mTSS at Week 26;
2. Proportion of subjects achieving LDA based on DAS28 (CRP) ≤ 3.2 at Week 12;
3. Change from baseline in DAS28 (CRP) at Week 12;
4. Change from baseline in HAQ-DI at Week 12;
5. ACR20 response rate at Week 12;
6. Proportion of subjects achieving LDA based on DAS28 (CRP) ≤ 3.2 at Week 12 (non-inferiority of Upadacitinib vs ADA);
7. Change from baseline in SF-36 Physical Component Score (PCS) at Week 12;
8. Proportion of subjects achieving LDA based on CDAI ≤ 10 at Week 12;
9. Change from baseline in morning stiffness (duration) at Week 12;
10. Change from baseline in FACIT-F at Week 12;
11. Proportion of subjects with no radiographic progression (defined as change from baseline mTSS ≤ 0) at Week 26.

Other key secondary endpoints (Upadacitinib versus placebo if not otherwise specified) for EU/EMA purposes are:

1. ACR50 response rate at Week 12
2. ACR70 response rate at Week 12

For binary endpoints, frequencies and percentages will be reported for each treatment group. Similar analyses as for the primary endpoint will be conducted. Additionally, for ACR50 response rate at Week 12, analysis will be conducted to test the non-inferiority of Upadacitinib versus ADA using the 95% confidence interval of treatment difference against a non-inferiority margin of 10% for US/FDA regulatory purposes. Similar non-inferiority analysis will be conducted for LDA based on DAS28 (CRP) at Week 12 with a 10% margin for EU/EMA regulatory purposes. Superiority of Upadacitinib vs ADA will also be tested using the Cochran-Mantel-Haenszel test adjusting for stratification factor prior bDMARD use.

For the major RA continuous endpoints DAS28 and HAQ-DI change from baseline, statistical inference will be conducted using analysis of covariance (ANCOVA) coupled with MI for missing data handling. Specifically, the ANCOVA model will include treatment as the fixed factor, and the corresponding baseline value and the stratification factor prior bDMARD use (Yes/No) as the covariates. For other continuous endpoints, statistical inference will be conducted using the MMRM model as described in Section 9.1.2, with the main stratification factor being prior bDMARD use (Yes/No). From both the MI and MMRM analyses, the LS mean and 95% CI will be reported for each randomized treatment group; the LS mean treatment difference and associated 95% CI and p-value will be reported comparing the Upadacitinib 15 mg group with the placebo group. For change from baseline in patient's global assessment of pain and change from baseline in HAQ-DI at Week 12, superiority of Upadacitinib vs ADA will also be tested.

Analyses for the mTSS-based key secondary endpoints are described in Section 9.3.2.

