9.2.1 Primary Efficacy Analysis

The primary endpoint for US/FDA regulatory purposes is the proportion of subjects achieving ACR20 response at Week 12. The primary endpoint for EU/EMA regulatory purposes is the proportion of subjects achieving CR based on DAS28(CRP) at Week 12. Analyses will be conducted separately for US/FDA regulatory purposes and EU/EMA regulatory purposes; for each set of analysis, only one primary endpoint is specified.

Analysis of the primary endpoint will be conducted on the FAS based on randomized treatment groups. Point estimate and 95% CI using normal approximation will be provided for the response rate for each randomized treatment group. Comparisons of the primary endpoint will be made between the Upadacitinib 15 mg QD group and the placebo group using the Cochran-Mantel-Haenszel test adjusting for stratification factor prior bDMARD use. Point estimate, 95% CI using normal approximation and p-value for

the treatment comparison will be presented. For the primary analysis, non-responder imputation (NRI) will be used.

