9.2.6 Efficacy Subgroup Analysis

The primary efficacy endpoint will be examined in the subgroups listed in [Table 7](#) below. Treatment difference between the Upadacitinib 15 mg group and the placebo group will be presented with point estimate and 95% confidence interval using normal approximation. No p-value will be provided for subgroup analysis. If any of the resulting subgroups has fewer than 10% of the planned study size (i.e., < 150 subjects), the subgroup analyses for that variable will not be presented.

Table 4. Subgroups for Efficacy Analysis

Subgroup Factor	Categories
Age	< 40, [40, 65), ≥ 65
Sex	Male or Female
Weight	< 60 kg or ≥ 60 kg
BMI	< 25 or ≥ 25
Race	White, Black or African American, American Indian or Alaska Native, Native Hawaiian or Other Pacific Islander, Asian, Other
Geographic Region	North America, South/Central America, Western Europe, Eastern Europe, Asia, Other
RA disease duration	< 5 year or ≥ 5 year
Baseline Rheumatoid Factor Status	Positive or Negative
Baseline Anti-CCP Antibody Status	Positive or Negative
Baseline both RF positive and Anti-CCP positive	Both Positive vs At Least One Negative
Baseline both RF negative and Anti-CCP negative	Both Negative vs At Least One Positive
Baseline DAS28[hsCRP)	< 5.1 or ≥ 5.1
Prior bDMARD use	Yes or No

9.2.7 Summary of Efficacy Analysis by Week 12

[Table 5](#) below provides the overview of the efficacy analyses by Week 12 to be performed on different endpoints.

Table 5. Summary of Efficacy Variables and Corresponding Analyses for Efficacy Analysis by Week 12

Efficacy Variables	Analysis Method
Primary Variables	

 • ACR20 response at Week 12^a • CR based on DAS28(CRP) at Week 12^b 	
 • Point estimate and 95% CI of the response rate for each treatment group. The 95% CI will be based on normal approximation. • Point estimate, 95% CI and p-value for the treatment comparison between Upadacitinib group and the placebo group, where the p-value is constructed using the Cochran-Mantel-Haenszel test adjusting for stratification factor prior bDMARD use. The 95% CI will be based on normal approximation. • Subgroup analysis. • Imputation: NRI for primary analysis and OC for sensitivity analysis • Analysis Set: FAS and Per Protocol Analysis Set as supportive analysis (NRI only).
Key Secondary Variables (Upadacitinib Versus Placebo if not Otherwise Specified)	

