
Binary Endpoints:
 
 • ACR50/70 response at Week 12 • ACR20 response at Week 12^b • LDA as measured by DAS28(CRP) at Week 12 • CR as measured by DAS28(CRP) at Week 12^a • LDA as measured by CDAI at Week 12 • ACR50 response at Week 12 (superiority of Upadacitinib vs ADA)^a 	
 • Point estimate and 95% CI of the response rate for each treatment group. The 95% CI will be based on normal approximation. • Point estimate, 95% CI and p-value for the treatment comparison between Upadacitinib group and the comparator groups using the Cochran-Mantel-Haenszel test adjusting for stratification factor prior bDMARD use. The 95% CI will be based on normal approximation. • Imputation: NRI for primary analysis and OC for sensitivity analysis • Analysis Set: FAS

Binary Endpoints (Non-inferiority of ABT-494 vs ADA):
 
 • ACR50 response rate at Week 12^a • Proportion of subjects achieving LDA based on DAS28(CRP) ≤ 3.2 at Week 12^b 	
 • 95% confidence interval of treatment difference against a non-inferiority margin of 10%. • Imputation: NRI for primary analysis and OC for sensitivity analysis • Analysis Set: FAS

Table 5. Summary of Efficacy Variables and Corresponding Analyses for Efficacy Analysis by Week 12 (Continued)

Efficacy Variables	Analysis Method
Key Secondary Variables (Upadacitinib Versus Placebo if not Otherwise Specified) (continued)	

Continuous Endpoints:
 
 • Change from baseline in DAS28(CRP) at Week 12 • Change from baseline in HAQ-DI at Week 12 • Change from baseline in HAQ-DI at Week 12 (superiority of Upadacitinib vs ADA).^a 	
 • LS mean, and 95% CI within each treatment group and LS mean, 95% CI and p-values between Upadacitinib group and the comparator groups using ANCOVA model with treatment, prior bDMARD use and baseline value as covariates. • Imputation: MI • Analysis Set: FAS

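### The EU non-inferiority interval for DAS28(CRP) low disease activity against adalimumab specifies no adjustment for baseline DAS28(CRP): a valid analysis that gives up a modest amount of precision

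*SAP*

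**What the plan says.** EU rank 6 in SAP 9.2.3 is "Proportion of subjects achieving LDA based on DAS28 (CRP) ≤ 3.2 at Week 12 (non-inferiority of Upadacitinib vs ADA"). The decision rule is given first for ACR50, "using the 95% confidence interval of treatment difference against a non-inferiority margin of 10" percent, and is then carried over to LDA: "Similar non-inferiority analysis will be conducted for LDA based on DAS28 (CRP) at Week 12 with a 10% margin for EU/EMA regulatory purposes". The non-inferiority row of Table 5 repeats it ("95% confidence interval of treatment difference against a non-inferiority margin of 10" percent), with NRI as primary, on the FAS. It names neither a covariate nor a formula for the interval.

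SAP 9.2.3 says binary key secondary endpoints are analysed like the primary endpoint. For that, SAP 9.2.1 promises "Point estimate, 95% CI using normal approximation and p-value for" the comparison. The only adjustment named for binary endpoints is in the "Cochran-Mantel-Haenszel test adjusting for stratification factor prior bDMARD use". Protocol 8.1.4.1.2 adds no covariate for the non-inferiority comparison.

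For change in DAS28, the same SAP section differs: "the ANCOVA model will include treatment as the fixed factor, and the corresponding baseline value and the stratification factor prior bDMARD use" enter together. Baseline DAS28(CRP) is also summarised in SAP 6.1 and is a subgroup factor in Table 4 ("Baseline DAS28[hsCRP"), so the variable will be derived in any case.

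**The concern.** LDA is a fixed cut-off, 3.2, on an absolute score and not a change from baseline. If baseline and Week 12 scores are correlated at all, a subject who starts lower is more likely to finish below the cut-off. Part of the outcome variance is then explained by a value already collected. The SAP uses that value when the score is analysed as a continuous variable and leaves it out when the score is cut at 3.2, without giving a reason.

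The test has a gatekeeping role. Under the step-down rule in SAP 9.2.5, missing non-inferiority at EU rank 6 closes ranks 7 to 11: SF-36 PCS, CDAI low disease activity, morning stiffness, FACIT-F and absence of radiographic progression. The comparison also uses the smallest arm, 300 adalimumab subjects. A wider interval than necessary raises the chance of a narrow miss, mainly if the two drugs are truly similar.

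**Working it through.** **Inputs from the documents.** Arms of 600 and 300 (SAP 4.2). LDA of 40% for upadacitinib and 35% for adalimumab, 10% dropout, and stated power of at least 90% (SAP 4.3, Protocol 8.2). Margin of 10 points and two-sided 95% interval (SAP 9.2.3). NRI on the FAS (Table 5).

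**Assumption.** The correlation ρ between baseline and Week 12 DAS28(CRP) is not in the documents. A range of 0.2 to 0.5 is used.

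**Step 1: the plan's own figure.** Power = Φ((0.10 + difference)/SE − 1.96), with unpooled SE.
- At 600/300: SE = √(0.40×0.60/600 + 0.35×0.65/300) = 0.0340. Power = Φ(0.15/0.0340 − 1.96) = 99.3%. The interval half-width is 1.96 × 0.0340 = 6.67 points.
- At 540/270, with dropouts removed: SE = 0.0359, power 98.7%.
- At 600/300 with dropouts counted as non-responders (36.0% versus 31.5%): SE = 0.0332, power 99.2%.

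The stated minimum of 90% holds with room to spare. It needs about 163 adalimumab subjects, or 182 after dropout, against 300 planned.

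**Step 2: the denominator.** NRI keeps every FAS subject and counts missing as non-response (SAP 9.1.2), so 600/300 is the relevant case.

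**Step 3: no true difference.** With 35% in both arms, SE = √(0.35×0.65×(1/600 + 1/300)) = 0.0337. Power = Φ(0.10/0.0337 − 1.96) = 84.3%.

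**Step 4: share of variance explained by baseline.** Under a bivariate-normal score, P(LDA | x) = Φ((c − ρx)/√(1 − ρ²)) with c = Φ⁻¹(p) and x the standardised baseline. Then R² = Var[P(LDA | x)]/[p(1 − p)], and the adjusted SE is the unadjusted SE × √(1 − R²). R² is shown at p = 0.35 and p = 0.40.

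| ρ | R² | Half-width, 40% vs 35% (points) | Interval narrower by | Power, 40% vs 35% | Power, 35% vs 35% |
|---|---|---|---|---|---|
| unadjusted | – | 6.67 | – | 99.3% | 84.3% |
| 0.2 | 2.4–2.5% | 6.59 | 1% | 99.4% | 85.1% |
| 0.3 | 5.5–5.6% | 6.48 | 3% | 99.5% | 86.2% |
| 0.4 | 9.8–10.0% | 6.33 | 5% | 99.6% | 87.7% |
| 0.5 | 15.5–15.8% | 6.13 | 8% | 99.8% | 89.7% |

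**Step 5: dilution by NRI.** Suppose 10% are imputed non-responders irrespective of baseline (an assumption) and the overall rate is still 35%. The rate in the other 90% is then 0.35/0.90 = 38.9%, and R² becomes 0.81 × Var[P(LDA | x)]/(0.35×0.65). This gives 2.1% at ρ = 0.2 and 13.3% at ρ = 0.5. Power at 35% in both arms is then 85.0% to 89.0%.

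**Step 6: simulation check.** In 1,500 trials per ρ at 600/300 and 40% versus 35%, the risk difference was standardised from a logistic model with treatment and baseline. The ratio of adjusted to unadjusted SE was 0.99, 0.98, 0.95 and 0.93 for ρ = 0.2, 0.3, 0.4 and 0.5. The mean adjusted estimate stayed between 4.9 and 5.1 points against a true 5, and at ρ = 0 nothing was gained or lost.

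**The case against.** The strongest reply is that nothing here is wrong. An interval for an unadjusted difference in proportions is valid, protocol and SAP agree on it, and baseline-adjusted ANCOVA or mixed models for continuous endpoints with CMH and normal-approximation methods for binary ones is a convention applied throughout. That stands: the proposal is an optional gain in efficiency.

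Other parts of the reply also stand:
- A reader might infer that the test is short of power. The plan's own assumptions do not support this (99.3%). The visible gain needs equal true rates, which the documents do not plan for.
- A reader might infer bias or an inflated type I error. Neither follows. Nor is chance imbalance in baseline disease activity a separate defect: under randomisation the unadjusted standard error already reflects it, so it is the same precision point.
- A reader might take baseline DAS28(CRP) to be a strong predictor. The documents do not show this, and at ρ = 0.2 the gain is about 1% of the width.
- That the interval is unadjusted is inferred from SAP 9.2.1 and from the absence of any covariate, since the non-inferiority row of Table 5 gives no formula. The adjacent binary row could be read as carrying the prior bDMARD stratification into the interval. On neither reading does baseline DAS28(CRP) enter.
- Baseline DAS28(CRP) need not exist for every subject. SAP 9.5.7 sets the score to missing if any component is missing, while the FAS requires only one dose. An adjusted model therefore needs a rule that the present analysis does not.

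What the reply does not remove is that the adjustment uses data already collected, leaves the marginal difference and the margin unchanged, and helps most when the drugs are similar.

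**Conclusion.** The point holds as a minor, optional improvement. No adjustment for baseline DAS28(CRP) is specified for the EU rank 6 interval, while the analysis of change in the same score has one. The cost is about 1% to 8% of interval width, equivalent to roughly 3% to 18% more subjects (1/(1 − R²) at R² of 2.5% and 15.5%). Power moves by less than one percentage point at the planned rates. At 35% in both arms it moves from 84.3% to 85.1–89.7%, or 85.0–89.0% with 10% imputed non-response. These sizes rest on the assumed correlation of 0.2 to 0.5, on the bivariate-normal working model, and on 600/300 analysed under NRI. The direction needs only a non-zero correlation.

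**What to change.** Before lock, amend SAP 9.2.3 and the non-inferiority row of Table 5 for LDA as follows.

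- Fit a logistic model with treatment, prior bDMARD use and baseline DAS28(CRP). Standardise it over the FAS subjects randomised to upadacitinib or adalimumab to obtain the marginal risk difference.
- Compare its 95% interval, by the delta method or bootstrap (state which), with the unchanged 10% margin. Keep NRI.
- Impute a missing baseline DAS28(CRP) by a simple rule blind to treatment, such as the overall baseline mean, so that no FAS subject is dropped.
- Report the unadjusted interval as a sensitivity analysis, and write down its formula.
- For consistency, the same model can serve LDA against placebo at EU rank 2.

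The cost is a few lines of SAP text and standard programming. No new data are needed, and the target quantity does not change.

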9.2.4 Exploratory Efficacy Analyses

Efficacy endpoints (Upadacitinib versus placebo and ADA) listed below will be summarized for all visits up to Week 12 by randomized treatment groups:

- Change from baseline in individual components of ACR response;
- ACR20/50/70 response rates;
- Change from baseline in DAS28(CRP) and DAS28 (ESR);
- Change from baseline in CDAI and SDAI;
- Proportion of subjects achieving LDA or CR based on DAS28 (CRP), DAS28 (ESR), Simplified Disease Activity Index (SDAI), and CDAI criteria (see below);
- Change from baseline in morning stiffness (severity and duration);
- Proportion of subjects with change from baseline in HAQ-DI ≤ -0.3 and ≤ -0.22 , respectively;
- ACR/EULAR Boolean remission;

	DAS28 (CRP) and DAS28 (ESR)	SDAI	CDAI
LDA	≤ 3.2	≤ 11.0	≤ 10
CR	< 2.6	≤ 3.3	≤ 2.8

9.2.5 Handling of Multiplicity

In order to preserve Type I error, a step-down approach will be used to test the primary and ranked key secondary endpoints where statistical significance can be claimed for a lower ranked endpoint only if the previous endpoint in the sequence meets the requirements of significance. Specifically, the testing will utilize the endpoint sequence of primary endpoint followed by ranked key secondary endpoints in the order as specified in Section 9.2.3, using α of 0.05.

9.2.6 Efficacy Subgroup Analysis

The primary efficacy endpoint will be examined in the subgroups listed in [Table 7](#) below. Treatment difference between the Upadacitinib 15 mg group and the placebo group will be presented with point estimate and 95% confidence interval using normal approximation. No p-value will be provided for subgroup analysis. If any of the resulting subgroups has fewer than 10% of the planned study size (i.e., < 150 subjects), the subgroup analyses for that variable will not be presented.

Table 4. Subgroups for Efficacy Analysis

Subgroup Factor	Categories
Age	< 40, [40, 65), ≥ 65
Sex	Male or Female
Weight	< 60 kg or ≥ 60 kg
BMI	< 25 or ≥ 25
Race	White, Black or African American, American Indian or Alaska Native, Native Hawaiian or Other Pacific Islander, Asian, Other
Geographic Region	North America, South/Central America, Western Europe, Eastern Europe, Asia, Other
RA disease duration	< 5 year or ≥ 5 year
Baseline Rheumatoid Factor Status	Positive or Negative
Baseline Anti-CCP Antibody Status	Positive or Negative
Baseline both RF positive and Anti-CCP positive	Both Positive vs At Least One Negative
Baseline both RF negative and Anti-CCP negative	Both Negative vs At Least One Positive
Baseline DAS28[hsCRP)	< 5.1 or ≥ 5.1
Prior bDMARD use	Yes or No

9.2.7 Summary of Efficacy Analysis by Week 12

[Table 5](#) below provides the overview of the efficacy analyses by Week 12 to be performed on different endpoints.

Table 5. Summary of Efficacy Variables and Corresponding Analyses for Efficacy Analysis by Week 12

Efficacy Variables	Analysis Method
Primary Variables	

 • ACR20 response at Week 12^a • CR based on DAS28(CRP) at Week 12^b 	
 • Point estimate and 95% CI of the response rate for each treatment group. The 95% CI will be based on normal approximation. • Point estimate, 95% CI and p-value for the treatment comparison between Upadacitinib group and the placebo group, where the p-value is constructed using the Cochran-Mantel-Haenszel test adjusting for stratification factor prior bDMARD use. The 95% CI will be based on normal approximation. • Subgroup analysis. • Imputation: NRI for primary analysis and OC for sensitivity analysis • Analysis Set: FAS and Per Protocol Analysis Set as supportive analysis (NRI only).
Key Secondary Variables (Upadacitinib Versus Placebo if not Otherwise Specified)	

Binary Endpoints:
 
 • ACR50/70 response at Week 12 • ACR20 response at Week 12^b • LDA as measured by DAS28(CRP) at Week 12 • CR as measured by DAS28(CRP) at Week 12^a • LDA as measured by CDAI at Week 12 • ACR50 response at Week 12 (superiority of Upadacitinib vs ADA)^a 	
 • Point estimate and 95% CI of the response rate for each treatment group. The 95% CI will be based on normal approximation. • Point estimate, 95% CI and p-value for the treatment comparison between Upadacitinib group and the comparator groups using the Cochran-Mantel-Haenszel test adjusting for stratification factor prior bDMARD use. The 95% CI will be based on normal approximation. • Imputation: NRI for primary analysis and OC for sensitivity analysis • Analysis Set: FAS

Binary Endpoints (Non-inferiority of ABT-494 vs ADA):
 
 • ACR50 response rate at Week 12^a • Proportion of subjects achieving LDA based on DAS28(CRP) ≤ 3.2 at Week 12^b 	
 • 95% confidence interval of treatment difference against a non-inferiority margin of 10%. • Imputation: NRI for primary analysis and OC for sensitivity analysis • Analysis Set: FAS

Table 5. Summary of Efficacy Variables and Corresponding Analyses for Efficacy Analysis by Week 12 (Continued)

Efficacy Variables	Analysis Method
Key Secondary Variables (Upadacitinib Versus Placebo if not Otherwise Specified) (continued)	

Continuous Endpoints:
 
 • Change from baseline in DAS28(CRP) at Week 12 • Change from baseline in HAQ-DI at Week 12 • Change from baseline in HAQ-DI at Week 12 (superiority of Upadacitinib vs ADA).^a 	
 • LS mean, and 95% CI within each treatment group and LS mean, 95% CI and p-values between Upadacitinib group and the comparator groups using ANCOVA model with treatment, prior bDMARD use and baseline value as covariates. • Imputation: MI • Analysis Set: FAS

 • Change from baseline in SF-36 Physical Component Score (PCS) at Week 12 • Change from baseline in morning stiffness (duration) • Change from baseline in FACIT-F • Change from baseline in patient's global assessment of pain at Week 12 (superiority of Upadacitinib vs ADA).^a 	
 • LS mean and 95% CI within each treatment group and LS mean, 95% CI and p-values between Upadacitinib group and the comparator groups using MMRM model with fixed effects of treatment, visit and treatment-by-visit interaction, prior bDMARD use and baseline value as covariate. • Analysis Set: FAS
Additional Variables (Summarized at all Visits up to Week 12)	

Binary Endpoints:
 
 • ACR20/50/70 response rate • LDA and CR based on DAS28(CRP), DAS28 (ESR), SDAI, and CDAI criteria • Proportion of subjects with change from baseline in HAQ-DI ≤ -0.3 and ≤ -0.22, respectively; • Boolean remission. 	
 • Point estimate and 95% CI of the response rate for each treatment group. The 95% CI will be based on normal approximation. • Point estimate, 95% CI and p-value for the treatment comparison between Upadacitinib group and the comparator groups using the Cochran-Mantel-Haenszel test adjusting for stratification factor prior bDMARD use. The 95% CI will be based on normal approximation. • Imputation: NRI for primary analysis and OC for sensitivity analysis • Analysis Set: FAS

Table 5. Summary of Efficacy Variables and Corresponding Analyses for Efficacy Analysis by Week 12 (Continued)

Efficacy Variables	Analysis Method
Additional Variables (Summarized at all Visits up to Week 12) (continued)	

Continuous Endpoints:
 
 • Change from baseline in individual ACR components • Change from baseline in DAS28 (CRP) and DAS28 (ESR) • Change from baseline in CDAI and SDAI • Change from baseline in morning stiffness (severity and duration) • Change from baseline in EQ-5D-5L • Change from baseline in SF-36 • Change from baseline in FACIT-F • Change from baseline in RA-WIS 	
 • LS mean and 95% CI within each treatment group and LS mean, 95% CI and p-values between Upadacitinib group and the comparator groups using MMRM model with fixed effects of treatment, visit and treatment-by-visit interaction, prior bDMARD use and baseline value as covariate. • Analysis Set: FAS

- a. US/FDA regulatory purposes.
b. EU/EMA regulatory purposes.

9.3 Efficacy Analysis for Period 1

Efficacy endpoints (Upadacitinib versus placebo and ADA) listed below will be summarized for all visits (that measurements are collected) in Period 1 by randomized treatment groups:

- Change from baseline in individual components of ACR response;
- ACR20/50/70 response rates;
- Change from baseline in DAS28(CRP) and DAS28 (ESR);
- Change from baseline in CDAI and SDAI;
- Proportion of subjects achieving LDA or CR based on DAS28 (CRP), DAS28 (ESR), Simplified Disease Activity Index (SDAI), and CDAI criteria (see below);
- Change from baseline in morning stiffness (severity and duration);

- Proportion of subjects with change from baseline in HAQ-DI ≤ -0.3 and ≤ -0.22 , respectively;
- ACR/EULAR Boolean remission;

	DAS28 (CRP) and DAS28 (ESR)	SDAI	CDAI
LDA	≤ 3.2	≤ 11.0	≤ 10
CR	< 2.6	≤ 3.3	≤ 2.8

Endpoints at Weeks 12, 26, and 48 are:

- Change from baseline in SF-36.
- Change from baseline in FACIT-F.
- Change from baseline in RA-WIS.
- Change from baseline in EQ-5D-5L.

Endpoints at Weeks 26 and 48 are:

- Change from baseline in mTSS;
- Proportion of subjects with no radiographic progression (defined as change from baseline in mTSS ≤ 0);
- Change from baseline in joint space narrowing score and joint erosion score.

9.3.1 Analysis of non-mTSS-Related Endpoints for Period 1

For continuous variables, statistical inference at each visit will be conducted using analysis of covariance (ANCOVA) with treatment and prior bDMARD use (Yes/No) as the fixed factor and the corresponding baseline value as the covariate. For subjects who meet the rescue criteria at either Week 14, 18, 22 or 26, data after rescue treatment switching will be overwritten by LOCF for the primary analysis. As observed (AO) data regardless of rescue treatment switching will also be summarized using descriptive statistics.

For binary endpoints, frequencies and percentages will be reported for each randomized treatment group. Similar analyses as for the primary endpoint will be conducted. For the primary analysis, non-responder imputation will be used. In addition, subjects who meet the rescue criteria (based on joint improvement) at either Week 14, 18 or 22 will be treated as non-responders at visits after rescue treatment switching. For subjects who meet the rescue criteria (based on CDAI LDA) at Week 26, data after rescue treatment switching will be overwritten by the last response prior to rescue. As observed (AO) data regardless of rescue will also be summarized using frequencies and percentages.

Plots by randomized treatment group over time (corresponding to the primary analysis described in this section) will be provided for selected efficacy parameters including ACR20/50/70, LDA and CR by DAS28(CRP) and CDAI, and change from baseline in DAS28(CRP), HAQ-DI and pain.

For the analyses and plots described in this section, all three randomized treatment groups: Upadacitinib 15 mg QD, PBO, and ADA 40 mg EOW, will be present up to Week 26; and only two treatment groups: Upadacitinib 15 mg QD and ADA 40 mg EOW, will be present from Week 26 to Week 48.

For Week 26 reporting, this set of analysis will only be presented up to Week 26 (as all subjects would have had a chance to reach Week 26 but not all subjects would have had a chance to reach Week 48 by the Week 26 database lock).

9.3.2 Analysis of mTSS-Based Key Secondary Endpoints at Week 26

For mTSS-based key secondary endpoints at Week 26, both linear extrapolation and As Observed (AO) analyses will be conducted. Linear extrapolation results will be used for the purpose of multiplicity control.

According to protocol, subjects who are rescued to a different study drug at the Week 14 visit will have x-ray collected at that visit, and subjects who prematurely discontinue study drug [REDACTED] will have x-ray collected at the PD visit. All

subjects who remain in the study at Week 26 will also have x-rays collected at the Week 26 visit. Available x-ray data will be assigned to the following analysis windows as defined in [Table 3](#): Baseline, Week 14, and Week 26.

In the linear extrapolation analysis, the Week 26 data will be imputed via linear extrapolation using x-ray from the baseline window and the Week 14 window for the following subjects: subjects rescued to a different study drug at Week 14, subjects who prematurely discontinued study drug [REDACTED] and subjects otherwise (i.e., not rescued to a different study drug at Week 14, not prematurely discontinued study drug [REDACTED] missing x-ray in the Week 26 window but have available x-ray in the Week 14 window.

In AO analysis, the observed Week 26 measurements will be used and attributed to the original randomized treatment groups regardless of treatment switching or study drug discontinuation.

For change from baseline in mTSS at Week 26, the point estimate and 95% CI will be reported for each randomized treatment group. Between-group comparisons for Upadacitinib 15 mg QD group and the placebo group will be performed using the analysis of covariance (ANCOVA) model with treatment and prior bDMARD use (Yes/No) as the fixed factors and the corresponding baseline value as the covariates. In the event that data severely deviates from the normal distribution, non-parametric analyses such as the Wilcoxon rank sum test may be considered for treatment comparison.

For proportion of subjects with no radiographic progression at Week 26, point estimate and 95% CI of the response rate for each randomized treatment group will be provided. Comparisons will be made between the Upadacitinib 15 mg QD group and the placebo group using the Cochran-Mantel-Haenszel test adjusting for prior bDMARD use (Yes/No). Point estimate, 95% CI and p-value for the treatment comparison will be presented.

9.3.3 Analyses of Additional mTSS-Related Endpoints for Period 1

For other mTSS-related endpoints at Week 26 and Week 48, analyses based on linear extrapolation and the As Observed (AO) analyses will be conducted. For Week 26 reporting, analysis of mTSS-related endpoints will only be presented up to Week 26.

For change from baseline in joint space narrowing score and joint erosion score at Week 26, linear extrapolation analysis and AO analysis will be performed similarly as described in Section 9.3.2.

According to protocol, subjects who are rescued to a different study drug at the Week 14 visit will have x-ray collected at that visit, and subjects who prematurely discontinue study drug [REDACTED] will have x-ray collected at the PD visit. All subjects who remain in the study at Week 26 will also have x-rays collected at the Week 26 visit, and all subjects who remain in the study at Week 48 will also have x-rays collected at the Week 48 visit. Available x-ray data will be assigned to the following analysis windows as defined in Table 3: Baseline, Week 14, Week 26, Week 36, and Week 48.

In the linear extrapolation analysis for Week 48 x-ray endpoints, the Week 48 data will be imputed via linear extrapolation for the following subjects: subjects who switched to a different study drug (by rescue at Week 14, 18, 22 or 26, or by switching from placebo to upadacitinib at Week 26), subjects who prematurely discontinued study drug [REDACTED] and subjects otherwise (i.e., not switched to a different study drug, not discontinued study drug [REDACTED] missing x-ray in the Week 48 window but have available post-baseline x-ray in an earlier analysis window. For those subjects who have switched study drug and/or prematurely discontinued study drug, x-ray data collected at treatment switching or at discontinuation of study drug will be used for extrapolation. For subjects otherwise missing observed x-ray in Week 48 window, available x-ray in the most recent analysis window (prior to the Week 48 window) will be used for extrapolation.

In the AO approach, the observed Week 48 measurements will be used and attributed to the original randomized treatment groups regardless of treatment switching or study drug discontinuation.

Similar statistical inference approach as described in Section 9.3.2 will be used.

9.3.4 Summary of Efficacy Analysis for Period 1

Table 6 below provides the overview of the efficacy analyses for Period 1 (including key secondary endpoints for mTSS) to be performed on different endpoints by randomized treatment group. For Week 26 reporting, this set of analysis will only be presented up to Week 26.

Table 6. Summary of Efficacy Variables and Corresponding Analyses for Efficacy Analysis for Period 1 (Including Key Secondary Endpoint for mTSS) (By Randomized Treatment Group)

Efficacy Variables	Analysis Method
Variables (Summarized at all Visits in Period 1)	
Binary Endpoints: 
 • ACR20/50/70 response rate • Proportion of subjects achieving LDA and CR based on DAS28(CRP), DAS28 (ESR), SDAI, and CDAI criteria • Proportion of subjects with change from baseline in HAQ-DI ≤ -0.3 and ≤ -0.22, respectively; • Boolean remission; • Proportion of subjects with no radiographic progression (defined as change from baseline in mTSS ≤ 0) at Weeks 26 and 48. 	
 • Point estimate and 95% CI of the response rate for each treatment group. The 95% CI will be based on normal approximation. • Point estimate, 95% CI and p-value for the treatment comparison between Upadacitinib group and the comparator groups using the Cochran-Mantel-Haenszel test adjusting for prior bDMARD use. The 95% CI will be based on normal approximation. • Plots by randomized treatment group over time • Imputation and treatment-switching handling for non-mTSS endpoints: NRI; AO for descriptive statistics • Imputation and treatment-switching handling for mTSS endpoints: linear extrapolation and AO • Analysis Set: FAS

Table 6. Summary of Efficacy Variables and Corresponding Analyses for Efficacy Analysis for Period 1 (Including Key Secondary Endpoint for mTSS) (By Randomized Treatment Group) (Continued)

Efficacy Variables	Analysis Method
Variables (Summarized at all Visits in Period 1) (continued)	
Continuous Endpoints: 
 • Change from baseline in individual ACR components • Change from baseline in DAS28 (CRP) and DAS28 (ESR) • Change from baseline in CDAI and SDAI • Change from baseline in morning stiffness (severity and duration) • Change from baseline in EQ-5D-5L • Change from baseline in FACIT-F • Change from baseline in RA-WIS • Change from baseline in SF-36 • Change from baseline in modified Total Sharp Score (mTSS) at Week 26 and Week 48 • Change from baseline in JSN and Joint Erosion at Week 26 and Week 48 	
 • LS mean and 95% CI within each treatment group and LS mean, 95% CI and p-values between Upadacitinib group and the comparator groups using ANCOVA model with treatment and prior bDMARD use as fixed factors and baseline value as covariate. Only nominal p-values will be provided. • Plots by randomized treatment group over time • Treatment-switching handling for non-mTSS endpoints: LOCF; AO for descriptive statistics. • Imputation and treatment-switching handling for mTSS endpoints: linear extrapolation and AO • Analysis Set: FAS

